# Clinical Investigation Plan (CIP)

Study Name: VivaSight-DL study (CIS-009)  
 Ethical committee number: S-20180081

CLI-000427

Rev. 02

## 18.3.3 Method of statistical analysis in relation to objectives

### Primary outcome:

- Number of times where fiberoptic confirmation of tube position during intubation or surgery is needed

If the observations are normally distributed, a student t-test will be used to examine if number of times the tube position needs to be verified with a bronchoscope is significantly different for procedures using VivaSight-DLT compared to a conventional DLT. If the observations are not normally distributed, a Mann-Whitney U test will be used.

### Secondary outcomes:

- Intubation time (sec)
  - If the observations are normally distributed, a student t-test will be used to examine if intubation time (sec) is significantly different for procedures using VivaSight-DLT compared to a conventional DLT. If the data is not normally distributed, transformation will be attempted to normalize the data. If the observations are still not normally distributed, a Mann-Whitney U test will be used.
- Number of intubation attempts
  - If the observations are normally distributed, a student t-test will be used to examine if number of intubation attempts is significantly different for procedures using VivaSight-DLT compared to a conventional DLT. If the observations are not normally distributed, a Mann-Whitney U test will be used.
- Number of times incorrect placement of the tube is prevented during intubation
  - If the observations are normally distributed, a student t-test will be used to examine if number of intubation attempts is significantly different for procedures using VivaSight-DLT compared to a conventional DLT. If the observations are not normally distributed, a Mann-Whitney U test will be used.
- Number of times the tube needs to be repositioned during intubation
  - If the observations are normally distributed, a student t-test will be used to examine if number of times the surgeon asked the tube placement to be confirmed is significantly different for procedures using VivaSight-DLT compared to a conventional DLT. If the observations are not normally distributed, a Mann-Whitney U test will be used.
- Number of times where the physician prevents repositioning of the tube during surgery
  - If the observations are normally distributed, a student t-test will be used to examine if number of intubation attempts is significantly different for procedures using VivaSight-DLT compared to a conventional DLT. If the observations are not normally distributed, a Mann-Whitney U test will be used.
- Number of times the tube needs to be repositioned during surgery
  - If the observations are normally distributed, a student t-test will be used to examine if number of times the surgeon asked the tube placement to be confirmed is significantly different for procedures using VivaSight-DLT compared to a conventional DLT. If the observations are not normally distributed, a Mann-Whitney U test will be used.
- Repositioning time (seconds) during surgery
  - If the observations are normally distributed, a student t-test will be used to examine if time used to reposition the tube is significantly different for procedures using VivaSight-DLT compared to a conventional DLT. If the data is not normally distributed, transformation will be attempted to normalize the data. If the observations are still not normally distributed, a Mann-Whitney U test will be used.
- Number of times the surgeon stops working while the tube is repositioned
  - If the observations are normally distributed, a student t-test will be used to examine if number of times the surgeon asked the tube placement to be confirmed is significantly different for procedures using VivaSight-DLT compared to a conventional DLT. If the observations are not normally distributed, a Mann-Whitney U test will be used.
- Time the backup anesthesiologist spends on the procedure
  - If the observations are normally distributed, a student t-test will be used to examine if time used to reposition the tube is significantly different for procedures using VivaSight-DLT compared to a conventional DLT. If the data is not normally distributed, transformation will be attempted to

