# Clinical Investigation Plan (CIP)

Study Name: VivaSight-DL study (CIS-009)  
Ethical committee number: S-20180081

CLI-000427

Rev. 02

- Number of intubation attempts
  - Intubation attempt is defined as the number of intubation attempts until successful intubation is accomplished. If the endotracheal tube is incorrectly placed and the tube is withdrawn from the subjects throat it counts as one attempt.
  - If more than three intubation attempts are used the intubation is defined as a failure and the subject is excluded from the study.
- Number of times incorrect placement of the tube is prevented during intubation
  - Prevention of repositioning is a corrective action that ensures optimal ventilation of the subject without having to move the tube after the bronchial cuff is inflated. An example of a corrective action during intubation could be change of the tube direction if it starts to enter the right main bronchi instead of the left main bronchi when advanced down the throat.
- Number of times the tube needs to be repositioned during intubation
  - In this study, repositioning is defined as the action where the bronchial cuff needs to be deflated to move the tube into the right position.
- Number of times where the physician prevents repositioning of the tube during surgery
  - Prevention of repositioning is a corrective action that ensures optimal ventilation of the subject without having to move the tube after the bronchial cuff is inflated. An example of a corrective action during surgery could be optimization of the cuff sealing by deflating and inflating the cuff without moving the tube.
- Number of times the tube needs to be repositioned during surgery.
  - In this study, repositioning is defined as the action where the bronchial cuff needs to be deflated to move the tube into the right position.
- Repositioning time (seconds) during surgery
  - In this study, repositioning is defined as the action where the bronchial cuff needs to be deflated to move the tube into the right position.
  - Time starts: when the syringe is attached to the valve to deflate the bronchial cuff
  - Time stops: when correct bronchial cuff placement is verified by capnography
- Rate of restriction on the surgical procedure during repositioning of the tube
  - One of the following statements is chosen:
    - Not restricted
      - The surgical procedure is not restricted at all, the surgeon continues to work full speed
    - Restricted

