## 18. DATA MANAGEMENT AND STATISTICAL ANALYSIS

### 18.1 Sample size

The following formula is used to validate that the chosen sample size is sufficient to detect an effect on the primary outcome):

$$n_1 \geq \left( \frac{(\sigma_{DLT}^2 + \sigma_{vivasight}^2) * (\lambda_z + \lambda_\beta)^2}{(\bar{x}_{DLT} - \bar{x}_{Vivasight})^2} \right)$$

Combined standard deviation and grand mean are based on three studies (2,12,13).

$$\begin{aligned} \bar{x}_{DLT} &= 0,37234 \text{ bronchoscopes used to correct DLT placement} \\ \bar{x}_{vivasight} &= 0,01087 \text{ bronchoscopes used to correct vDLT placement} \\ \sigma_{DLT}^2 &= 0,23622 \text{ bronchoscopes} \\ \sigma_{vivasight}^2 &= 0,01087 \text{ bronchoscopes} \end{aligned}$$

We set power to 90% thus the  $\lambda_\beta = 1.28$  and significance level at 5%  $\rightarrow \frac{0.05}{2} = 0,025 \rightarrow \lambda_z = 1,96$

Thereby, to reject the  $H_0$  the sample size must be:

$$\begin{aligned} n_1 &\geq \left( \frac{(0,23622 + 0,01087) * (1,96 + 1,28)^2}{(0,37234 - 0,01087)^2} \right) = 19,852 \text{ patients} \\ N &= 19,852 * 2 = 39,7035 \rightarrow 40 \text{ patients} \end{aligned}$$

Therefore, a total sample size (N) of 40 generates a power of 90%. A sample size of 50 patients allows a potential dropout rate of 20 percent.

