### Secondary outcomes:

- Intubation time (seconds)
  - There must be a time difference between the DLT entering the patient and the correct DLT positioning is verified. Must be stated in seconds.
- Number of intubation attempts
  - Must be stated in integers.
- Number of times incorrect placement of the tube is prevented during intubation
  - Must be stated in integers.
- Number of times the tube needs to be repositioned during intubation
  - Must be stated in integers
- Number of times where the physician prevents repositioning of the tube during surgery
  - Must be stated in integers.
- Number of times the tube needs to be repositioned during surgery
  - Must be stated in integers and the reposition time must be positive in cases where repositioning has been reported
- Reposition time (seconds) during surgery
  - The time must be positive in cases where that the tube has been repositioned.
- Number of times the surgeon stops working while the tube is repositioned

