### Data collection

Type of surgery	Date of surgery	Knife start (hh:mm)	Knife end (hh:mm)
 Open  Keyhole			

**Intubation** (the period from the direct laryngoscope is introduced into the subject's mouth until correct bronchial cuff placement is verified by capnography)

Bronchoscope use (n)	Repositioning prevented (n)	Tube repositioned (n)	Intubation attempts (n)	Intubation time (sec)
				sec.

Cormack-L classification	Smooth intubation?	Need to bend tube?	Resistance during tube placement?	Need of suction after tube placement?
 1  2  3  4	 Yes  No			

Bronchial cuff pressure	Tracheal cuff pressure	Comments:
Cm H 2 O	Cm H 2 O	

**Surgery** (the period from correct bronchial cuff placement is verified by capnography until the DLT exits the subject's mouth)

Bronchoscope use (n)	Repositioning prevented (n)	Tube repositioned (n)

Repositioning of tube	Time used to reposition the tube	Rate of restriction on the surgical procedure	Responsible anesthesiologist assisted	Time spend by responsible anesthesiologist
1 st repositioning	sec	 Not restricted  Restricted  Completely restricted	 Yes  No	sec
2 nd repositioning	sec	 Not restricted  Restricted  Completely restricted	 Yes  No	sec
3 rd repositioning	sec	 Not restricted  Restricted  Completely restricted	 Yes  No	sec

Extubation of the subject	Smooth extubation?	Did the subject cough?	Did the subject complain of throat pain?
	 Yes  No	 Yes  No	 Yes  No

Comments:

Any adverse events/adverse device effects?		
Yes	No	If yes: please specify (if SAE or SADE please fill out SEA or SADE form):

Any complications in relation to airway management?		
Yes	No	If yes: please specify:

Any general complications?		
Yes	No	If yes: please specify:

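### Repositioning time is recorded only when the tube is repositioned, and the plan gives no value for other patients and no rule for repeated times, so the between-arm test most naturally compares subsets formed after randomisation.

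*Combined protocol and SAP*

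**What the plan says.** Repositioning time during surgery is a secondary endpoint. Section 4 defines its start: "Time starts: when the syringe is attached to the valve to deflate the bronchial cuff". It ends when capnography verifies cuff placement, and section 7.6 gives the same interval. The Case Report Form (Appendix V) has a column "Time used to reposition the tube" with one row per repositioning, for up to three.

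Section 18.3.3 plans a comparison between arms to examine "if time used to reposition the tube is significantly different for procedures using VivaSight-DLT compared to a conventional DLT": a t-test if the data are normal, otherwise transformation, otherwise Mann-Whitney U. The only rule on values is in section 18.5: "The time must be positive in cases where that the tube has been repositioned". Nothing states what value a patient without a repositioning receives, which patients enter the test, or how two or three times from one patient become one observation.

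Three other parts of the plan bear on this:
- The number of repositionings during surgery is a separate secondary endpoint with its own test (sections 4 and 18.3.3).
- Section 18.3.2 allows regression imputation or listwise deletion for missing values.
- Section 2 names time and need for repositioning among the outcomes that drive cost, and section 18.7 feeds an average cost per procedure into the model.

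**The concern.** A time that exists only after a repositioning is conditional on a post-randomisation event. The introduction presents the integrated camera as a means of securing better placement, so the device is expected to change who is repositioned. If it prevents the easy repositionings and leaves the hard ones, the arm with fewer repositionings can show the longer mean time. Randomisation does not protect against this, whatever the repositioning rate.

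Three practical consequences follow:
- The number of observations is unplanned and may be very small in the test arm.
- The result is not the quantity the economic evaluation needs, which is time per procedure including procedures with no repositioning.
- Section 18.3.2 does not separate a patient who was not repositioned from a patient whose time was lost. A literal application could impute times for events that never happened.

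**Working it through.** **The plan's own figure.** Section 18.1 uses planning means of 0.37234 ("bronchoscopes used to correct DLT placement") and 0.01087 ("bronchoscopes used to correct vDLT placement"), and the variance sum "0,23622 + 0,01087".

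n per arm = 0.24709 × (1.96 + 1.28)² / (0.37234 − 0.01087)² = 0.24709 × 10.4976 / 0.13066 = 19.85.

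Twice this is 39.70, so 40, and 40 / (1 − 0.20) = 50. The stated sample size reproduces. It concerns bronchoscope use only; repositioning time has no sample-size basis in the documents.

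**What the conditional test estimates.** For each arm:

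mean time per procedure = (probability of any repositioning) × (mean total time given at least one).

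A test on recorded times addresses at most the second factor, and only in patients selected through the first. The cost per procedure depends on the product.

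**How many test-arm observations there could be.** Let p be the share of test-arm patients with at least one repositioning during surgery. The documents do not give p, so it is an assumption and is varied. With n = 25 (section 5.2):

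P(none) = (1 − p)^25, and P(at most one) = (1 − p)^25 + 25p(1 − p)^24.

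For the last column, the smallest two-sided exact Mann-Whitney p-value without ties, for m test and k control patients with one value each, is 2 / C(m + k, m). With m = 1 and k = 9 this is 2/10 = 0.20; with m = 2 and k = 9 it is 2/55 = 0.036. The column gives the chance that m and k allow p ≤ 0.05 at all (unadjusted). It takes the control probability as 0.37234, again a proxy, which implies 25 × 0.37234 = 9.3 control patients.

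| Assumed p, test arm | Expected patients | P(none) | P(at most one) | P(0.05 attainable) |
|---|---|---|---|---|
| 1.087% | 0.27 | 76.1% | 97.0% | 2.4% |
| 5% | 1.25 | 27.7% | 64.2% | 30% |
| 10% | 2.5 | 7.2% | 27.1% | 66% |
| 20% | 5.0 | 0.4% | 2.7% | 95% |

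If only 20 per arm remain, the 20% dropout that section 18.1 allows for, P(none) is 80.4% at 1.087% and 12.2% at 10%. The chance that 0.05 is attainable is then 1.0% and 44%.

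No test-arm data is the more likely outcome only if p is below 1 − 0.5^(1/25) = 2.7% with n = 25, or 1 − 0.5^(1/20) = 3.4% with n = 20.

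**Why 1.087% is only a proxy.** It is a bronchoscope-use rate. Section 7.6 lets a repositioning be confirmed on the monitor, so test-arm repositionings can occur without a bronchoscope and p may be higher. In the other direction, section 18.1 does not limit the rate to surgery, while this endpoint is limited to surgery.

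**The case against.** The strongest reply is that the plan is silent rather than wrong. The section 18.5 rule requires a positive time only where there was a repositioning, which leaves room for zero elsewhere. Scoring zero would keep the randomised comparison. Section 18.3.3 speaks of procedures and each subject takes part once (section 5.1), which is compatible with one value per procedure. The count of repositionings is tested separately, so a reader would see frequency beside duration. The cost model draws on summed process costs and tracked personnel time (sections 7.10 and 18.7), not on this test, and the recorded times can be averaged per procedure whatever test is used.

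Much of this stands:
- A reader might infer that the plan treats several times from one patient as independent. No section says so; the rule is simply absent.
- A reader might also infer from the planning figures that the test arm would usually have no data. That requires taking the bronchoscope-use rate as a repositioning rate, which the documents do not do.
- The economic model is not invalidated by this test.

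The reply does not remove the point. If zero was intended, it has to be written down before data are seen, because recorded times alone are the natural input to a test described in these words. A separate test of counts shows the imbalance in frequency but does not correct the selection in the conditional comparison.

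**Conclusion.** The point holds as a gap in specification with a clear risk. As written, the analysis most naturally compares repositioned patients only. That is not a comparison of the randomised arms and does not estimate time per procedure. This conclusion needs no assumed rate. It would fall away only if patients without a repositioning were meant to count as zero, which the documents do not state.

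The size of the data problem is conditional. Over assumed test-arm rates from 1.1% to 20%, the chance of no test-arm observation among 25 runs from 76% to 0.4%. Sparse data are a real possibility; absent data are not established. The issue is confined to secondary endpoints, and the primary analysis and N = 50 are unaffected.

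**What to change.** In section 18.3.3, define the endpoint as total repositioning time per patient during surgery: the sum over repositionings, and 0 seconds if there was none. State in section 18.3.2 that no repositioning is a zero and not a missing value, so that imputation applies only to times that should have been recorded. Analyse all analysed randomised patients; the wording needs that limit because sections 6.4 and 6.5 remove the data of withdrawn and excluded subjects. Compare arms by a permutation test on the mean difference, with a bootstrap confidence interval. Report time per repositioning descriptively, with the number of patients and of repositionings in each arm.

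Apply the same zero rule to back-up anaesthesiologist time, but reconcile its definitions first. Section 4 runs it from answering the phone to leaving the operating room, section 7.6 from the call until the tube is repositioned, and the Case Report Form records it by repositioning. The description of its test in section 18.3.3 also repeats the repositioning-time wording and should be corrected.

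For repositioning time, the cost is wording only. The form already holds the data for up to three repositionings per patient; it should say where a fourth would be recorded. The downside is that the new variable has many zeros and mixes frequency with duration, so it should be read beside the count endpoint. With many zeros, a rank test would largely repeat the comparison of counts, which is a reason to prefer the mean difference.

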      - The surgical procedure continues but with limited speed, the surgeon's ability to perform the procedures is affected.
    - Completely restricted
      - The surgical procedure is completely restricted (surgical procedure is paused), the surgeon is not able to work at all.
- Number of times the backup anesthesiologist is called into the operating room for assistance
- Time the back-up anesthesiologist spends on the procedure
  - Time starts: when the backup anesthesiologist answers the phone
  - Time stops: when the backup anesthesiologist leaves the operating room

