## Clinical Investigation Plan (CIP)

Study Name: VivaSight-DL study (CIS-009)  
Ethical committee number: S-20180081

CLI-000427

Rev. 02

In case the needs to be repositioned during the surgery, *the number of times the tube is repositioned during the surgery must be recorded in the CRF*. If the tube needs to be repositioned, the subsequent steps should be followed:

1. Deflate the bronchial cuff unless lung separation is absolutely required during this time.
  - *Record whether the surgeon need to stop the procedure while the tube is repositioned in the CRF.*
  - *If the responsible anaesthesiologist is called for assistance to repositioning the tube it is recorded in the CRF*
2. Reposition the tube
3. Confirm correct tube position by looking at the aView monitor or with the use of FOB.
  - *If fiberoptic bronchoscopy is needed to confirm position, the number of times the fiberoptic bronchoscope (FOB) is used must be recorded in the CRF:*
    - Apply lubrication and antifogging agents to the FOB if needed.
    - The FOB is placed through the tracheal lumen.
    - The FOB is advanced, and the carina is identified.
    - The bronchial lumen of the tube must be visualized entering the left main stem bronchus.
4. The bronchial cuff is inflated under direct vision and should lie just distal to the carina.
5. Confirm correct bronchial cuff placement by capnography (CO2 return and SaO2)
  - *The time it takes to reposition the tube is recorded in the CRF (from syringe is attached to the valve to deflate the bronchial cuff until the bronchial cuff placement is confirmed).*
  - *If the responsible anaesthesiologist is called for assistance, the time from calling the responsible anaesthesiologist for backup until the tube is repositioned is recorded in the CRF.*

If a repositioning of the tube is prevented, *the number of times the repositioning is prevented must be recorded in the CRF*.

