# Clinical Investigation Plan (CIP)

Study Name: VivaSight-DL study (CIS-009)  
 Ethical committee number: S-20180081

CLI-000427

Rev. 02

- Must be stated in integers, reposition time must be positive and in must be reported that a tube needs to be repositioned
- Number of times the backup anesthesiologist is called into the operating room for assistance
  - Must be stated in integers
- Time the back-up anesthesiologist spends on the procedure
  - No predetermined pass/fail criterion

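### The three-level surgical-restriction endpoint has no test of its own: sections 18.3.3 and 18.5 analyse a count of surgeon stops, and the test sentence names yet another variable.

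*Combined protocol and SAP*

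**What the plan says.** Four places in the combined protocol and SAP describe how surgery is disrupted while the tube is repositioned.

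- **Section 4, secondary end-points.** The endpoint is "Rate of restriction on the surgical procedure during repositioning of the tube", with one of three statements chosen. The middle level reads "The surgical procedure continues but with limited speed, the surgeon's ability to perform the procedures is affected". The top level reads "The surgical procedure is completely restricted (surgical procedure is paused), the surgeon is not able to work at all".
- **Section 7.6, Surgery.** The recording instruction is "Record whether the surgeon need to stop the procedure while the tube is repositioned in the CRF", which is a yes/no question about stopping.
- **Appendix V, Case Report Form.** The column "Rate of restriction on the surgical procedure" has three tick boxes, one per level, in each of three repositioning rows.
- **Sections 18.3.3 and 18.5.** The outcome is "Number of times the surgeon stops working while the tube is repositioned". Section 18.3.3 assigns a t-test, or a Mann-Whitney test if the data are not normal, but the sentence doing so says the test will examine whether the "number of times the surgeon asked the tube placement to be confirmed is significantly different" between devices. Section 18.5 sets the data rule: "Must be stated in integers, reposition time must be positive and in must be reported that a tube needs to be repositioned".

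Section 18.3.1 adds that categorical data in general are summarised as frequencies and percentages. Section 18.3.4 makes all tests two-sided at 5% and applies a Bonferroni correction without giving the number of tests.

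**The concern.** The endpoint that is defined and collected is not the variable that is analysed. By section 4's own definitions only *Completely restricted* means that the surgeon stops. A repositioning that slows the operation adds nothing to a stop count, so the patient scores the same as one whose tube was never moved.

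Even the stop count is not cleanly specified, because the test sentence beneath it refers to requests for confirmation. An analyst would have to choose among the three-level rating, the stop count and the confirmation requests, possibly after seeing the data. Section 18.2 has all data analysed at the sponsor, which makes it more important to settle the choice beforehand. The alternative hypothesis in section 3 rests on workflow optimisation, and slowed surgery is a workflow effect that the trial records but does not plan to test.

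**Working it through.** **1. The mismatch, side by side**

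| Place | Variable | Is *Restricted* distinguished? |
|---|---|---|
| Section 4 | three-level rating per repositioning | yes |
| Section 7.6 | did the surgeon need to stop | no |
| CRF, Appendix V | three tick boxes per repositioning | yes |
| 18.3.3, outcome name | count of stops | no |
| 18.3.3, test sentence | requests to confirm placement | no; a different quantity |
| 18.5 | integer count of stops | no |

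The confirmation-request wording also appears in 18.3.3 under the two entries for the number of repositionings (during intubation and during surgery). That points to a copied sentence. The CRF has no field for such requests.

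**2. The plan's only power figure**

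Section 18.1 concerns bronchoscope use: n = (0.23622 + 0.01087) × (1.96 + 1.28)² / (0.37234 − 0.01087)² = 0.24709 × 10.4976 / 0.13066 = 19.85 per arm. That gives 39.70, rounded up to 40, and 40 / (1 − 0.20) = 50. The figure reproduces, but it says nothing about this endpoint. The documents give no repositioning rate, severity split or power for surgical restriction.

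**3. Illustration under assumed rates**

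From the plan: 25 per arm, two-sided 5%, Mann-Whitney (tie-corrected here). Assumed: the bronchoscope-use means 0.372 and 0.011 are borrowed as the probability of one repositioning, and the three levels are equally likely.

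- Expected patients with a stop: 25 × 0.372/3 = 3.1 v 25 × 0.011/3 = 0.09.
- Expected patients with *Restricted* or worse: 25 × 0.372 × 2/3 = 6.2 v 25 × 0.011 × 2/3 = 0.18.
- If a control patients and no test patients have a stop, the tie-corrected statistic is z² = 49a/(50 − a). For a = 3 this is 3.13, below 3.84; for a = 4 it is 4.26. About four stops are needed where about three are expected.

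Simulated power (the merged score gives 0 to no repositioning or *Not restricted*, 1 to *Restricted*, 2 to *Completely restricted*; the four-level score separates the two groups scored 0):

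| Repositioning; severity split (%) | Stop | Merged | Four-level | Any repositioning (yes/no) |
|---|---|---|---|---|
| 37.2% v 1.1%; equal thirds | 36% | 84% | 97% | 98% |
| 37.2% v 10%; equal thirds | 19% | 43% | 63% | 66% |
| 37.2% v 1.1%; 20/30/50 | 65% | 91% | 97% | 98% |

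The four-level score does no better than a plain yes/no for any repositioning. Its advantage over the merged score therefore comes from repositioning frequency, which 18.3.3 already lists as a separate endpoint.

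**4. Sensitivity to the assumptions**

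Here repositionings per patient are Poisson with means 0.372 and 0.011, so fewer control patients have any: 1 − e^(−0.372) = 31%. Splits are *Not restricted*/*Restricted*/*Completely restricted*, equal in both arms.

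| Split (%) | Stop count | Merged score |
|---|---|---|
| 10/10/80 | 86% | 90% |
| 20/20/60 | 70% | 85% |
| equal thirds | 31% | 77% |
| 10/80/10 | 1% | 89% |

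If instead both arms have a mean of 0.8 and the device turns stops into slowdowns (20/20/60 v 20/70/10), the order reverses: 79% for the stop count v 17% for the merged score. With an assumed 10 tests (alpha 0.005), the 20/20/60 row falls to 19% v 39%.

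**The case against.** **Nothing is lost from the data.** All three levels are on the CRF and section 18.3.1 would allow a frequency table. This stands: what is missing is a named test of the endpoint as defined, not the information.

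**The endpoint is secondary and unpowered.** This also stands. Under a Bonferroni correction power may be low whichever variable is used, so the case rests on specification rather than on power.

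**A stop count may be the better variable.** It can be, if the device chiefly turns stops into slowdowns (79% v 17% above). This is a reason to report stops alongside the rating. It does not justify leaving the variable open, since the choice could decide the result.

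Two stronger readings are tempting, and the documents support neither.

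- *A reader might infer that counting stops throws away most of the power.* No rates for this endpoint are given. Across the assumptions tried, the loss runs from 4 points (86% v 90%) to nearly all power (1% v 89%), and it can reverse.
- *A reader might infer that workflow cost will be undercounted.* Section 7.10 collects costs by process mapping and tracked personnel and procedure times, the CRF records knife start and end, and repositioning time is its own endpoint. The effects listed for the model in section 18.7 are bronchoscope need and cross-infection. No passage feeds the stop count into cost.

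**Conclusion.** The plan is wrong as written on this endpoint. Section 4 and the CRF define and collect a three-level rating. Sections 18.3.3 and 18.5 put a stop count in its place, section 7.6 asks only about stopping, and the test sentence names a variable that is neither listed nor collected. Followed literally, the plan never tests this secondary endpoint as defined. That conclusion rests on the text alone.

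The size of the consequence is uncertain. The 36% v 84% comparison assumes bronchoscope-use rates as a stand-in for repositioning, equal severity thirds in both arms, 25 patients per arm and no multiplicity correction. It shows what could happen and is not an estimate for this trial. The primary endpoint and the sample size are unaffected.

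**What to change.** - In 18.3.3 and 18.5, replace the stop count with the three-level rating, taken as each patient's worst level during surgery.
- Score patients with no repositioning together with *Not restricted*, so that the score does not simply re-test repositioning frequency.
- Compare arms with the Mann-Whitney test that the plan already names, with tie correction, or with a proportional-odds model. State which.
- Report the number of complete stops per arm alongside it.
- Correct the copied test sentence so that it names the variable being tested.
- Align the recording instruction in section 7.6 with the three CRF boxes.

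The cost is wording only, since the CRF already collects the rating. The limitation to accept is that a worst-level score has little power against a shift from stops to slowdowns, which is why stops should be shown beside it.
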